### Safety Outcome Measures

- Side Effects Checklist (SEC; physician administered) – (*all visits*)
- Columbia Suicide Severity Rating Scale – (*all visits*)
- Iowa Gambling Task – (*baseline, week 6, week 12*)
- Vital signs including blood pressure (standing/supine) – (*all visits*)
- Electrocardiogram (ECG) – (*screening, week 6, week 12*)
- Liver function tests; chemistry panel; CBC; urinalysis – (*screening, week 12*)
- Pregnancy test for women of childbearing age – (*screening, week 12*)
- Urine toxicology – (*screening, week 12*)
- Medication log of current medications and all medications administered during previous week – (*all visits*)

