bearing potential who are not using a medically accepted means of contraception (including oral contraceptive or implant, condom, diaphragm, spermicide, intrauterine device, tubal ligation, or partner with vasectomy) **10.** Women who are breastfeeding. **11.** Participation in any other investigational cognitive enhancement study within 30 days.

**Concomitant Medications:** Practical and ethical considerations prevent a focus on medication-free patients. Medications with known adverse cognitive effects will be disallowed (i.e., topiramate, anticholinergics), as will agents that may enhance cognition (e.g., amphetamine, other DA agonists). Benzodiazepines will not be allowed within 6 hours of testing. ECT in the past 12 months will be disallowed, as will any drug known to interact with pramipexole. With regard to antipsychotic medications specifically, only half of the sample will be allowed to be taking any antipsychotics. Recruitment efforts will be adjusted to ensure 50% of the sample is antipsychotic-free at baseline. Further, we will exclude any subject who is taking more than 4 concomitant psychotropic medications. Older generation neuroleptics will be specifically disallowed due to their high binding potential at the D2 receptor (Kapur et al. 1999). Although some of the standard treatments for BD (e.g. lithium) may influence cognition, it is impractical to exclude these medications given their widespread use; therefore, data will be coded for medication classes and dosages to determine a load score (as per Hassel et al. 2008) to be included as a covariate in statistical analyses.

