### e) Study Endpoints

The primary endpoints related to the safety and efficacy on neurocognitive functioning of pramipexole will be measured. Neurocognitive performance on the MATRICS Consensus Cognitive Battery will be measured at baseline, week 6, and 12 (or end of study). Safety measures will be assessed at each visit throughout the study. Co-primary measures of everyday functioning (described below) will be assessed at baseline and week 12 (or end of study).

|   |   |  |
|---|---|--|
|  | Protocol Title:                           | 1/2-Pramipexole in Bipolar Disorder: Targeting Cognition (PRAM-BD) |
|   | Principal Investigator Name/Contact Info: | [name]   |
|   | Primary Contact Name/Contact Info:        | [name]
[contact]                          |
|   | Date Revised:                             | March 23, 2016 – date of IRB approval May 6, 2017                  |
|   | Study Number:                             | GCO 13-0237, HS 14-00328   |

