## f) Procedures Involved in the Human Research

All eligible participants will undergo study visits at screening, baseline (week 0), week 1, week 2, week 3, week 4, week 6, week 8, and week 12, (end of study).

Randomization will be conducted via a computer generated program and all study staff will be blinded unless un-blinding is required for safety reasons. Subjects will be randomized on a 1:1 ratio with stratification for concomitant antipsychotic status and depression at baseline (HRSD <8 vs  $\geq$  8). Study drug will be blinded and matched to placebo. Adapting from our previous work in BD and according to package labeling, the dosage titration schedule will be slow and flexible. Dosing will be initiated at 0.25 mg QHS on night one, followed by 0.25 mg BID day two onward, and increased every week to a target of 4.5 mg/day. As compared with our previous maximum 1.5 mg/day ([name] et al. 2012), we opted to allow up to 4.5 mg/day (the maximum approved dosage in Parkinson’s disease) to ensure adequate target engagement. We are familiar with this dose range, as 4.5 mg/day was allowed in our study in BD depression (Goldberg et al. 2004). Dosing will be flexible based on side effects; however, if 1.5 mg/day cannot be tolerated, the subject will be discontinued. Titration will occur up to week 6 and then efforts will be made to maintain the same dose until the completion of the trial (week 12).

Measures are described in detail below:

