***MSSM Additional Monitor:***

*Indicate whether this person is the PI, a Team Member, or is Independent: Team Member (co-investigator)*

*Last Name: [name]*

*First Name: [name]*

*Academic Title: Associate Professor*

*Department: Psychiatry*

*Mailing Address: [name]*

*[contact]*

*[contact]*

*E-mail: [contact]*

*2. [name] has been responsible for running two previous studies using this agent in bipolar disorder (Goldberg et al 2004; [name] et al 2012).*

*3. Adverse events, subject compliance with the protocol, and drop outs will be monitored for safety.*

*4. **ACCUMULATED** safety and data information (items listed in number 3 above and interim analysis of efficacy outcomes) will be reviewed by the monitors or the Data Monitoring Committee (DMC) twice a year.*

*5. Alteration of the study design is not expected; however, SAEs will be considered for unblinding and relatedness to drug will be assessed.*

*6. In order to minimize toxicity we are only allowing up to a max of the FDA recommended dose – dosing is flexible based on AEs and tolerability.*

*7. There will be no specialized grading system used to evaluate adverse events.*

*8. Procedures that will be used to assure data accuracy and completeness include double data entry and frequent queries of database.*

*9. Should a temporary or permanent suspension of your study occur, in addition to the PPHS, we will report the occurrence to NIH as well as ZHH, the other site conducting study.*

|   |   |  |
|---|---|--|
|  | Protocol Title:                           | 1/2-Pramipexole in Bipolar Disorder: Targeting Cognition (PRAM-BD) |
|   | Principal Investigator Name/Contact Info: | [name]   |
|   | Primary Contact Name/Contact Info:        | [name]
[contact]                          |
|   | Date Revised:                             | March 23, 2016 – date of IRB approval May 6, 2017                  |
|   | Study Number:                             | GCO 13-0237, HS 14-00328   |

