### **11) Payment to Subjects**

Participants will be informed during the consent process of the study compensation. Participants will be paid \$100 for the screening visit; \$50 for baseline and week 6; \$20 for week 1, 2, 3, 4, 8; \$100 for week 12. Total possible payment of \$400 for study completion.. Screen failures will receive the screening rate (\$100) provided they undergo study procedures at that visit.

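### The medication log looks back one week, but visits after week 4 are two to four weeks apart, so a short drug course between visits need not be recorded

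*Combined protocol and SAP*

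**What the plan says.** The medication log is listed in Section 5(f), Safety Outcome Measures, for all visits. Its content is "Medication log of current medications and all medications administered during previous week".

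The opening of Section 5(f) gives the visit schedule. After weekly visits up to week 4 it continues "week 4, week 6, week 8, and week 12, (end of study"). The payments in Section 11 match: one rate applies "for week 1, 2, 3, 4, 8", with separate amounts for baseline, week 6 and week 12. No visit is scheduled or paid at weeks 5, 7, 9, 10 or 11.

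Several parts of the plan rely on knowing what participants took:

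- Section 5(b), Concomitant Medications: "Medications with known adverse cognitive effects will be disallowed (i.e., topiramate, anticholinergics), as will agents that may enhance cognition". The same paragraph bars ECT in the past year, "as will any drug known to interact with pramipexole".
- Section 5(i), MSSM Additional Monitor, item 3: "Adverse events, subject compliance with the protocol, and drop outs will be monitored for safety".
- The same list, item 5: "SAEs will be considered for unblinding and relatedness to drug will be assessed".

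**The concern.** A one-week look-back suits weekly visits. Here the schedule widens after week 4 and the look-back does not widen with it. A participant could start and finish a short course of a barred drug between two visits, answer every log question truthfully, and leave no trace of it in the log.

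The gap is largest in weeks 6 to 12, the period in which Aim 2 sets out to assess longer-term safety. An adverse event from, say, week 9 could be reported at week 12 while a brief drug course that might explain it lies outside the period the log covers. A breach of the concomitant-medication rules could be missed in the same way.

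**Working it through.** The plan gives no figure for log coverage, so there is nothing of its own to reproduce. The check is interval arithmetic on the schedule.

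**Inputs.** Visits at weeks 0, 1, 2, 3, 4, 6, 8 and 12 (Section 5(f); payments in Section 11 agree). Look-back of one week plus current medications (Section 5(f), Safety Outcome Measures).

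**Uncovered time in weeks.** For each interval, uncovered = max(0, gap − 1). Gaps are 1, 1, 1, 1, 2, 2, 4, so uncovered time is 0, 0, 0, 0, 1, 1, 3. The total is 5 of 12 weeks (41.7%): weeks 4–5, 6–7 and 8–11. One of these weeks precedes week 6 and four follow it.

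**Uncovered time in days.** Visit days are 7, 14, 21, 28, 42, 56 and 84. The answer depends slightly on how the week is counted.

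- A, visit day is one of the seven: days 29–35, 43–49 and 57–77 are missed. 7 + 7 + 21 = 35 of 84 (41.7%).
- B, visit day plus the seven days before it: days 29–34, 43–48 and 57–76 are missed. 6 + 6 + 20 = 32 of 84 (38.1%).

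The longest course that can escape is therefore 20 to 21 days.

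**Chance that a course escapes, if one occurs.** A course of D days escapes only if it fits wholly inside one window of W days, which allows max(0, W − D + 1) start days. The plan gives neither course lengths nor timing, so D is varied and start days are assumed equally likely over the 84 days.

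| D (days) | Missed start days, A | Missed start days, B | Share of 84 |
|---|---|---|---|
| 3 | 5 + 5 + 19 = 29 | 4 + 4 + 18 = 26 | 31.0–34.5% |
| 7 | 1 + 1 + 15 = 17 | 0 + 0 + 14 = 14 | 16.7–20.2% |
| 14 | 0 + 0 + 8 = 8 | 0 + 0 + 7 = 7 | 8.3–9.5% |

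The denominator also matters. Counting only 7-day courses that lie wholly within the 84 days leaves 78 start days, giving 14/78 to 17/78 (17.9–21.8%).

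**By period, 7-day course.**

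- Weeks 0–6: 0/36 to 1/36 (0–2.8%), counting courses wholly within the period.
- Weeks 6–12: 14/36 to 16/36 (38.9–44.4%) on the same basis, or 14/42 to 16/42 (33.3–38.1%) if every course starting in those weeks is counted.

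**Cognitive testing.** Section 5(e) places post-baseline MCCB testing at weeks 6 and 12. Days 36–42 and 78–84 are covered under either convention, so the week before each test is recorded.

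**Other sources.** Urine toxicology is at screening and week 12 only. Section 5(h) says that medical-record information may be collected, which guarantees nothing. The eligibility condition that no medication change is planned (Section 5(b)) is an intention at entry, not a record. Section 6 calls the visits weekly, but the schedule and payments do not support that after week 4. Nothing in the plan calls for a diary, a since-last-visit question or a medication review between visits.

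**The case against.** The strongest case on the other side concerns weight. The primary endpoint is change to week 6, only one uncovered week precedes it, and the analysis is intent-to-treat. Any drug begun in a gap and continued is picked up as current. What remains is a brief course of unknown frequency in patients selected for a stable regimen. All of that stands, and it limits the importance of the point.

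The log line also sets what must be asked and does not stop staff from writing down an earlier drug that a participant mentions. That is fair: such a course need not be recorded, which is weaker than saying it never would be.

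The log is not the only safety route either. Site investigators review safety data as they arise, the DSMB reviews reportable serious events, and a physician rates side effects at each visit. A serious event would probably prompt a fuller drug history, so the attribution point is weaker for serious events than for others. But none of these routes is a medication record, and the plan does not require one of them to supply it.

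The percentages rest on uniform start days and a choice of denominator, hence the ranges above. The day counts need neither assumption.

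**Conclusion.** The gap is real and minor. As written, the log leaves 32 to 35 of 84 days unreached, about 5 of 12 weeks, with 4 of the 6 weeks between weeks 6 and 12 among them. If a 7-day course occurs and start days are equally likely, it escapes in roughly 17–22% of cases overall and 33–44% in weeks 6–12, depending on the counting convention and denominator. How many such courses would occur cannot be said from the plan.

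The consequence is an incomplete record for checking disallowed and interacting drugs and, mainly for non-serious events, for adverse-event attribution in the long-term safety period. No bias in the primary efficacy estimate is shown.

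**What to change.** In Section 5(f), Safety Outcome Measures, have the log record current medications and all medications taken since the last visit. Formally uncovered time between baseline and week 12 then falls from 5 weeks to 0.

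The cost is one line on the case report form and no added visit. The drawback is longer recall: two weeks at weeks 6 and 8, and four weeks at week 12, in a sample enrolled for cognitive impairment. Capture will therefore be imperfect, but better than leaving those weeks unasked.

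As an editorial matter only, Section 6 should refer to scheduled rather than weekly visits, to agree with Section 5(f).

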### Clinical/Symptom Measures

- Structured Clinical Interview for the DSM-IV (SCID-IV) – (*screening*)
- Symptom rating scales: Young Mania Rating Scale (YMRS); Hamilton Rating Scale for Depression (HRSD); Brief Psychiatric Rating Scale (BPRS) – (*all visits*)
- Smoking questionnaire – (*screening, baseline, week 6, week 12*)

|   |   |  |
|---|---|--|
|  | Protocol Title:                           | 1/2-Pramipexole in Bipolar Disorder: Targeting Cognition (PRAM-BD) |
|   | Principal Investigator Name/Contact Info: | [name]   |
|   | Primary Contact Name/Contact Info:        | [name]
[contact]                          |
|   | Date Revised:                             | March 23, 2016 – date of IRB approval May 6, 2017                  |
|   | Study Number:                             | GCO 13-0237, HS 14-00328   |

Neurocognitive/Functional Measures

- Screening cognitive battery (see inclusion criteria 4.) – (*screening*)
- Cognitive assessment: MATRICS Consensus Cognitive Battery (MCCB- plus; see description below) – (*baseline, week 6, week 12*)
- The Probabilistic Stimulus Selection Task – (*baseline, week 6, week 12*)
- UCSD Performance Skills Assessment (UPSA) – (*baseline, week 12*)
- The World Health Organization Disability Assessment Schedule (WHODAS 2.0) – (*baseline, week 12*)

| The MATRICS Consensus Cognitive Battery | Domain               | Note/Description               |
|---|-----------------------------|---------------------------------------|
| Category Fluency                                      | Speed of Processing         | Total animals in 60 seconds           |
| BACS Symbol Coding                                    | Speed of Processing         | Matching numbers to symbols           |
| Trail Making Test Part A                              | Speed of Processing         | Dot-to-dot: Numbers only              |
| CPT-Identical Pairs                                   | Attention/Vigilance         | Computerized numeric stimuli          |
| Letter-Number Span                                    | Working Memory              | Recoding numbers and letters in order |
| WMS-III Spatial Span                                  | Working Memory              | Visual sequence forward and backward  |
| Hopkins Verbal Learning (HVLT)                        | Verbal Learning             | 12 word list x 3                      |
| Brief Visuospatial Memory Test (BVMT)                 | Visual Learning             | 6 designs to be drawn from recall     |
| NAB Mazes   | Reasoning & Problem Solving | Pencil-paper maze solutions           |
| MSCEIT Managing Emotions                              | Social Cognition            | Situational social judgments          |
| Additional Measures (“Plus”)            | ---                         | ---                                   |
| Affective Go-no-go                                    | Affective Neuroscience      | Emotional modulation of inhibition    |
| Emotional Stroop                                      | Affective Neuroscience      | Affective Bias/Cognitive Control      |

|   |   |  |
|---|---|--|
|  | Protocol Title:                           | 1/2-Pramipexole in Bipolar Disorder: Targeting Cognition (PRAM-BD) |
|   | Principal Investigator Name/Contact Info: | [name]   |
|   | Primary Contact Name/Contact Info:        | [name]
[contact]                          |
|   | Date Revised:                             | March 23, 2016 – date of IRB approval May 6, 2017                  |
|   | Study Number:                             | GCO 13-0237, HS 14-00328   |

### **g) Specimen Banking**

N/A

### **h) Data Management and Confidentiality**

If a participant agrees to be in this study, we will collect health information that identifies them [“Protected Health Information” (PHI)]. We may collect the results of tests, questionnaires and interviews. We may collect information from a patient’s medical record. We will only collect information that is needed for the research. This information is described in the consent form. By signing the consent form a participant gives us permission (authorization) to collect, use and share their health information.

Data collected will include questionnaires and assessments as described above in section (5f). Labs and tests will be performed at the MSMC laboratory and information sent to the PI. These data will be stored in a binder which will be secured in a double locked fashion. Blood samples will be labeled with de-identified codes, which cannot be associated with individual subjects. PHI, such as patient name and DOB, will only be included in a separate file including the consent documents. The file linking de-identified data with participant PHI will be stored on an encrypted drive. PHI data will be stored indefinitely, as well as for potential future research. All other data collected for the study will be de-identified and stored apart from PHI, identified by a study number linked to PHI in a secure file. This data will be stored indefinitely.

The PI will be responsible for receipt and transmission of study data and specimens. Quality control of the data collected will include double data entry and data quality checks by investigators after each 5 subjects completed.

Study staff will have access to data and records and these may be reviewed by the Mount Sinai School of Medicine Institutional Review or government agencies (i.e. NIH) in order to meet federal or state research regulations. Participants will be made aware in the consent process that once private information is disclosed, it is subject to re-disclosure by the recipient and can no longer be considered protected. If research records are used for decisions related to clinical care, then a participant has the right to review this information and to request changes. This is limited to information about their treatment, and does not include information related to procedures or tests that are for research purposes only. Participants may access this information only after the study analysis is complete.

Data from this study may be used in medical publications or presentations. The information will be de-identified so that individual subjects cannot be recognized and the information will no longer be considered PHI. The information that is collected for research will be analyzed for many years and it is not possible to know how long this

|   |   |  |
|---|---|--|
|  | Protocol Title:                           | 1/2-Pramipexole in Bipolar Disorder: Targeting Cognition (PRAM-BD) |
|   | Principal Investigator Name/Contact Info: | [name]   |
|   | Primary Contact Name/Contact Info:        | [name]
[contact]                          |
|   | Date Revised:                             | March 23, 2016 – date of IRB approval May 6, 2017                  |
|   | Study Number:                             | GCO 13-0237, HS 14-00328   |

analysis and follow-up will take. Therefore, participants are allowing access to this information indefinitely.

Participants will only be identified with a numerical code in compliance with HIPAA regulations. Raw subject data will be secured in double locked physical control. Digitized raw data will be similarly de-identified using coding and will be secured on an MS SQL server with Windows-integrated security.

**Statistical Methods: Preliminary analyses:** Groups will be compared on demographics, baseline symptom ratings, and concomitant medication load; if necessary, covariates will be included in subsequent models. MCCB data are standardized using the MCCB program, scores are age- and sex- corrected and reported on a t-score scale (Mean=50, SD=10). Any study focusing on improving cognition must consider practice effects (Goldberg et al. 2008). The placebo arm will provide estimates of expected practice so that we are able to calculate a reliable change index (RCI) to determine the meaningfulness of change (Goldberg et al. 2009).

**Primary hypothesis testing:** 100 participants will be randomized in a 1:1 allocation to treatment with pramipexole or placebo. The primary assessment of safety will be based on the incident of adverse event rates and standardized mood ratings at each visit. Differences in the incidence of individual adverse events will be compared between randomization arms using Poisson regression. Exact 95% confidence intervals (based on the Poisson distribution) for the risk ratios for individual adverse events for treatment with pramipexole versus placebo will be computed and may incorporate an estimated overdispersion parameter if observed variability exceeds that determined by the Poisson distribution. Performance on the IGT will also be used to track potential changes in impulse-control (baseline, weeks 6 and 12). We will test for correlations between IGT performance and mania symptoms at the times of testing (simultaneous measurements). Moreover, we will use IGT change scores as predictors in regression models to evaluate changes in mania ratings at concurrent time points as well as future time points. This will directly address the question of whether or not changes in IGT strategy serve as markers of current mania and/or impending affective destabilization.

The relative specificity of pramipexole in binding to D2/D3 receptors allows for a unique opportunity to enhance DA in neural networks associated with specific aspects of cognition as well a reward processing, which will be carefully assayed in this study so that exploratory analyses will be able to test questions related to the role for these receptors across several interacting domains in BD, at least at the level of behavior. Exploratory analyses will include specific domains and individual tasks which will be modeled to account for main effects and interactions (as described in primary analyses below).

The primary outcome for efficacy is change in cognition from baseline to week 6 (MCCB Composite). The null hypothesis is that there is no difference in this change between

|   |   |  |
|---|---|--|
|  | Protocol Title:                           | 1/2-Pramipexole in Bipolar Disorder: Targeting Cognition (PRAM-BD) |
|   | Principal Investigator Name/Contact Info: | [name]   |
|   | Primary Contact Name/Contact Info:        | [name]
[contact]                          |
|   | Date Revised:                             | March 23, 2016 – date of IRB approval May 6, 2017                  |
|   | Study Number:                             | GCO 13-0237, HS 14-00328   |

patients on pramipexole vs. patients on placebo. This will be tested in an intent-to-treat analysis using a 0.05 level two-tailed test based on a mixed effects regression model, with patients considered to be a random effect, and randomization group a fixed effect. In order to preserve statistical power, change in MCCB Composite will be used as the dependent variable; however, secondary analyses will be conducted for MCCB domain scores and measure of reward processing. The use of two post baseline evaluations (weeks 6 and 12) and the ability of the model to incorporate all available data, also improves efficiency (i.e., power). This approach will also be employed in subsequent comparisons of specific domains and for measures of reward processing. These additional analyses will be conducted at a nominal 0.05 level and will focus on enhancing interpretation of the primary analysis by highlighting the specific domains most affected by pramipexole. Since randomization is stratified by concomitant antipsychotic use and baseline depression status, indicators of stratification will be included in the model as fixed effects.

*Missing data:* Although the mixed effects modeling approach allows patients with evaluations at week 4 but missing at week 8 to be included, bias may be introduced if missing data are related to patient response. For example, it may be that patients responding poorly are less likely to have a week 8 evaluation than those patients with better response. The mixed effects analysis would weigh the results of these poorly performing patients less (as they provide fewer data) and in the presence of a positive effect of pramipexole, decrease power. To assess the extent that any bias has been introduced by missing data, we will impute missing week 8 values. Note that if no bias is produced by the missing data, analyses with and without imputation should provide virtually identical results. If the analyses produce different results, we will work to identify the causes by comparing patients with and without missing data. Based on our prior trial experience we expect relatively few patients (< 10) to be missing the week-8 visit due to attrition. Patients with missing data will have their 8 week MCCB score imputed via multiple imputation assuming that the data are MAR, i.e., the missing nature of the variable is independent of the value of the variable given the observed data. The specific imputation model to be used will be determined prior to examination of any outcome data, but will include MCCB score at baseline and at 4 weeks. Separate imputations will be done for each randomization group.

*Due to the 12 week course of the study, mixed models will still be utilized for variables collected with sufficient frequency; however, when incorporating missing data, we will only be able to do so when at least two time points are included. Subjects with only baseline data will be included in descriptive analyses but will be dropped for analyses where necessary.*

|   |   |  |
|---|---|--|
|  | Protocol Title:                           | 1/2-Pramipexole in Bipolar Disorder: Targeting Cognition (PRAM-BD) |
|   | Principal Investigator Name/Contact Info: | [name]   |
|   | Primary Contact Name/Contact Info         | [name]
[contact]                          |
|   | Date Revised:                             | March 23, 2016 – date of IRB approval May 6, 2017                  |
|   | Study Number:                             | GCO 13-0237, HS 14-00328   |

**Sample size/Power:** A total of one hundred patients will be randomized 1:1 (50 from ISMMS, 50 from ZHH). The adequacy of this sample size is based on the ability to reject the null hypotheses of no difference between treatment groups with respect to the MCCB composite score with sufficient power (80%). Ideally, sample size would be determined to ensure adequate power to detect the minimal clinically important difference. No specific guidelines exist to establish such a threshold in this setting but cognitive change of at least a moderate effect would likely be necessary to allow for clinical meaningfulness. Our sample size provides approximately 80% power to detect a standardized difference (e.g., Cohen’s d) of approximately 0.55 with a two-tailed 0.05 level test. For the pre-specified subgroup analysis based on concomitant use at baseline, the detectable standardized difference is about 0.80.

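### Beyond the stratification indicators, covariates enter the efficacy models only if a baseline comparison of the arms makes them necessary, with no criterion or timing set; medication load is conditional in one section and unconditional in another

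*Combined protocol and SAP*

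**What the plan says.** Four statements bear on which covariates enter the efficacy models.

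- Section 5(h), Preliminary analyses: "Groups will be compared on demographics, baseline symptom ratings, and concomitant medication load; if necessary, covariates will be included in subsequent models". The later models include the primary test. The sentence gives no threshold, no list of covariates to be added, no decision-maker and no time by which the decision is made.
- Section 5(h), Primary hypothesis testing: "indicators of stratification will be included in the model as fixed effects". This is unconditional. Section 5(f) names the factors: "stratification for concomitant antipsychotic status and depression at baseline".
- Section 5(b), Concomitant Medications: a medication load score is "to be included as a covariate in statistical analyses", again without condition.
- Section 5(h), on the outcome: "change in MCCB Composite will be used as the dependent variable", tested "using a 0.05 level two-tailed test based on a mixed effects regression model". MCCB scores are already corrected for age and sex. The description of the primary model does not list baseline MCCB Composite, site or the load score.

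**The concern.** Under randomisation, a baseline difference between arms is a chance event. It carries no information on whether the variable predicts change in the MCCB Composite. A rule that admits covariates on observed imbalance can leave out a strong predictor that happens to be balanced and take in a useless one that happens to differ.

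The rule is also open. *Necessary* is undefined, and nothing requires the choice to precede sight of the outcomes. The Missing data paragraph of the same section does impose that discipline on the imputation model, so the safeguard was known and was not applied here.

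The statements on medication load cannot all be followed. Section 5(b) puts the score in the models. Section 5(h) puts it among the variables compared before any covariate is added, and the primary model does not mention it. A reader cannot write down the primary model from the text.

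Two things are at stake: precision in a trial with about 78% power at its design effect, and a single primary p-value that should come from one model fixed in advance.

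**Working it through.** **1. The plan's own figure.** Inputs from section 5(h): 100 patients randomised 1:1 (50 per arm), d about 0.55, two-sided 0.05, power about 80%. For an unadjusted comparison, power ≈ Φ(d√(n/2) − 1.96) = Φ(0.55 × 5 − 1.96) = Φ(0.79) = 78.5%. The noncentral t gives 77.7%. The stated figure therefore reproduces, and it takes no credit for covariates.

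**2. How often arms look different by chance.** The trigger p < 0.05 is my assumption, because the plan sets none. With k independent variables, the chance of at least one trigger is 1 − 0.95^k: 14.3% for k = 3 and 26.5% for k = 6.

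**3. What fixed adjustment could give.** If covariates explain a share R² of the variance of change, d becomes d/√(1 − R²). The documents give no R².

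- R² = 0.05: 80.6%
- R² = 0.10: Φ(5 × 0.55/√0.90 − 1.96) = Φ(0.94) = 82.6%
- R² = 0.20: Φ(5 × 0.55/√0.80 − 1.96) = Φ(1.11) = 86.7%

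Baseline MCCB is a special case. With equal variances and baseline-to-follow-up correlation ρ, adjusting the change score for baseline multiplies its variance by (1 − ρ²)/[2(1 − ρ)] = (1 + ρ)/2. Taking 0.55 in units of the SD of change, power is 80.6% at ρ = 0.9, 82.6% at 0.8, 84.7% at 0.7 and 86.7% at 0.6. These formulas ignore the degrees of freedom spent, so simulated gains are smaller.

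**4. Simulated power at d = 0.55.** Independent candidates with equal correlation r with the outcome, so R² = k r²; 50 per arm; 4,000 to 5,000 trials per setting. The imbalance rule adds a candidate if its baseline t test has p < 0.05.

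| Candidates | R² | No candidates | Imbalance rule | All fixed | Fixed minus rule |
|---|---|---|---|---|---|
| 6, r = 0.10 | 0.06 | 78.0% | 77.8% | 77.5% | −0.3 |
| 3, r = 0.20 (strata in model) | 0.12 | – | 78.7% | 81.7% | 3.0 |
| 6, r = 0.15 | 0.135 | 78.4% | 77.4% | 80.7% | 3.3 |
| 6, r = 0.20 | 0.24 | 76.6% | 77.6% | 85.0% | 7.4 |
| 6, r = 0.20 (strata in model) | 0.24 | 76.5% | 76.8% | 85.2% | 8.4 |

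A further run at R² = 0.24 with strata in the model gave 6 to 7 points. The simulation standard error of one power figure near 0.8 is √(0.8 × 0.2/5000) = 0.6 points, so these runs are compatible with a gain of about 7. Where it could be compared, the rule sits within about a point of using no candidates at all.

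**5. Simulated type I error.**

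- Mechanical rule: 4.5% with six candidates at r = 0.2 and strata in the model; 4.6% and 4.1% with three candidates at R² = 0.1 and 0.2. Across all settings tried with strata in the model, the range was 3.3 to 5.1%.
- Smallest p among the strata-only, single-covariate and full models: 8.0% with three candidates at r = 0.2 and 9.9% with six at r = 0.2.

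**The case against.** The strongest reply is that the conditional rule is only part of the covariate plan. A reader might infer from the Preliminary analyses sentence that no covariate enters without an imbalance. The documents do not support that: both stratification indicators enter unconditionally, the load score is unconditional in section 5(b), and age and sex are corrected in the T-scores. The rule is left with the remaining demographics, the symptom ratings (depression being partly covered by the HRSD stratum) and load as section 5(h) treats it. This reply stands and sets the scope of the point.

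A reader might also infer that the written rule inflates the false-positive rate. It does not: applied mechanically it is at or slightly below 5%. The 8 to 10% belongs to a different procedure, taking the smallest p over several models, which the plan does not describe. The comparison is placed under preliminary analyses, ahead of the models. What remains is that nothing excludes such a choice.

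Third, the size of the power gain rests on assumptions about the number, independence and strength of covariates. With weak covariates (R² = 0.06) there is no gain. Six candidates at r = 0.3 would give far larger gains, but they imply R² = 6 × 0.09 = 0.54, for which the documents offer no basis.

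None of this supplies a criterion or a time for the decision, or resolves the conflict over medication load.

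**Conclusion.** The point holds within these limits. Apart from the stratification indicators, section 5(h) selects covariates on chance imbalance, by an undefined standard and at an unspecified time, and it contradicts section 5(b) on medication load.

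The cost of the mechanical rule is forgone precision: about 0 to 7 points of power at d = 0.55 for an assumed R² of 0.06 to 0.24, with type I error at about 3 to 5%. The cost of leaving the choice open is a type I error of roughly 8 to 10% at worst over the same range. That is a bound on discretion, not a forecast. Both rest on an assumed p < 0.05 trigger and on three to six independent candidates.

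It would be wrong to conclude that the planned power of about 80% is broken. That figure is for an unadjusted comparison; the rule passes up a possible gain and takes nothing from it.

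**What to change.** In section 5(h), Preliminary analyses, delete the clause that makes covariates conditional on the baseline comparison. Before unblinding, fix the covariates of the primary model by their expected relation to MCCB change:

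- the two stratification indicators;
- baseline MCCB Composite;
- site;
- the medication load score, as section 5(b) states.

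Use that model whatever the baseline table shows, and present the table descriptively. Label any model adjusted for an observed imbalance as a sensitivity analysis that cannot replace the primary result. Bring section 5(b) and the Preliminary analyses and Primary hypothesis testing paragraphs of section 5(h) into agreement.

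The cost is wording and a few degrees of freedom, with little or no gain in power if the chosen covariates prove weakly prognostic.
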